#### **10.1.2. Primary Efficacy Measure**

The primary efficacy endpoint is OS, defined as the time from the date of randomization to the date of death from any cause. For patients not known to have died as of the data cut-off date, OS time will be censored at the last contact date the patient was known to be alive prior to the cut-off date.

### 10.1.3. Secondary Efficacy Measures

The following secondary efficacy measures (Table JBAS.10.1) will be collected at the times shown in the Study Schedule (Attachment 1).

**Table JBAS.10.1. Secondary Efficacy Endpoints**

Endpoint	Definition
TTP	The time from the date of study randomization to the date of first observation of objective progression. For patients who are not known to have progressed as of the data-inclusion cut-off date, TTP will be censored at the date of the last objective progression-free disease assessment
PFS (based on RECIST v1.1)	The time from the date of study randomization to the date of first observation of objective progression or death from any cause, whichever occurs first. For patients who are not known to have died or progressed as of the data-inclusion cut-off date, PFS time will be censored at the date of the objective progression-free disease assessment
ORR (based on RECIST v1.1)	The proportion of patients who achieved a best overall response of either complete or partial response defined by RECIST v1.1. The ORR for each treatment group will be estimated by dividing the total number of confirmed responders by the number of patients who received at least 1 dose of study treatment

Abbreviations: ORR = objective response rate; PFS = progression-free survival; RECIST = Response Evaluation Criteria in Solid Tumors; TPP = time-to-tumor progression; v = version.

## 10.2. Health Outcome/Quality of Life Measures

### 10.2.1. Patient-Reported Outcomes

The assessment of PROs, including disease-specific symptoms and health-related quality of life, will be assessed using the EORTC QLQ-30 and QLQ HCC-18.

#### EORTC QLQ-30

The EORTC QLQ-C30 is a general measure of quality of life in cancer patients (Aaronson et al. 1993). It is a self-reported instrument consisting of 30 items covered by 1 of 3 dimensions: global health status/quality of life (2 items); functional scales (15 total items addressing either physical, role, emotional, cognitive, or social functioning); symptom scales (13 total items addressing either fatigue, nausea/vomiting, pain, dyspnea, insomnia, appetite loss, constipation, diarrhea, or financial impact) (Attachment 11).

#### EORTC QLQ HCC-18

To assess disease-specific symptoms of HCC patients, the HCC-specific module (EORTC QLQ HCC 18) will be used. The EORTC QLQ HCC18 is an 18-item HCC-specific supplemental module developed to augment QLQ-C30 and to enhance the sensitivity and specificity of HCC-related QOL issues (Blazeby et al. 2004) (Attachment 12).

Both the EORTC QLQ-30 and QLQ HCC-18 will be administered at baseline, at every cycle starting from Cycle 2, and at discontinuation (see Study Schedule for details [Attachment 1]).

PRO instruments should be completed at the beginning of office visits, before any extensive contact and consultation with the clinician/study investigator or staff. Consultation with the clinician may bias perceptions about quality of life and symptoms and thus affect assessments.

The EORTC QLQ-30 and QLQ HCC-18 will only be completed by patients for whom there is a validated language translation in which the patient is fluent.

### 10.2.2. Resource Utilization

Investigators will be asked to document the use of best supportive care measures, concomitant medications, transfusions, and treatment-related hospitalization days. Such assessments are to be taken throughout the study through the 30-day safety follow-up visit.

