### 6.3. Exploratory Objectives

- to explore markers associated with EMT transformation and the TGF- $\beta$ -associated signaling pathway presence in the original diagnostic tumor tissue and optional posttreatment tumor tissue and the correlation of this with both clinical efficacy endpoints and biomarker response
- to explore TTP, PFS, and ORR by immune response RECIST (irRECIST)
- to explore tumor volume changes of measurable lesions on CT/MRIs obtained for tumor response as an assessment of treatment effects on biological growth rate
- to explore the relative effects of LY2157299 versus LY2157299 plus sorafenib versus sorafenib plus placebo on antiangiogenesis as assessed by dynamic contrast-enhanced MRI (DCE-MRI) metrics and on tumor cellularity/cell death as assessed by diffusion-weighted MRI (DW-MRI) metrics. These exploratory MRI techniques will only be performed at clinical sites where the associated MRI center scanner has been qualified prior to patient enrollment by the imaging core laboratory designated by the sponsor.
- to explore fibrosis-related tests, such as fibrotest
- to assess healthcare resource utilization including transfusions and hospitalizations

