The investigator (or qualified designee) must document his/her review of the ECG printed at the time of evaluation, the final overread ECG report issued by the central ECG laboratory, and any alert reports.

Other safety measures include assessments of physical examinations, preexisting conditions, transfusions and hospitalizations, and AEs. Patients will be assessed before each visit by using the CTCAE version 4.0.

For patients in the extension period, monitoring should be performed at predose on Day 1 of every other cycle for patients receiving galunisertib. The standard care of treatment should be followed for patients receiving sorafenib.

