### **12.2.11. Safety Analyses**

All safety summaries and analyses will be based upon the Safety Population as defined in Section [12.2.1](#).

Overall exposure to study drug, the numbers of patients completing each cycle, and the dose intensity will be summarized using descriptive statistics. The number of patients with any dose adjustment will be presented for entire treatment period as well as for each cycle. The number of patients with dose reductions, dose delays, or dose omissions will also be summarized, as will the reasons for dose adjustments.

An overall summary of AEs will be provided for AEs deemed by the investigator to be possibly related to study medication and will be repeated for events regardless of study drug causality. Incidence rates of these events will be compared between treatment arms using Fisher's exact test.

Safety analyses will include, but are not limited to, the following:

- all reported AEs, including seriousness, severity, and possible relationship to study drug, using CTCAE terminology and grades
- TEAEs, including seriousness, severity, and possible relationship to study drug, using CTCAE terminology and grades
- dose adjustments for any study therapy
- physical examination and other safety observations, including those specifically targeting the monitoring of cardiac safety
- laboratory measures

AE terms and severity grades will be assigned by the investigator using CTCAE version 4.0. MedDRA version 16 (or higher) will be used when reporting AEs by MedDRA terms. The MedDRA lower level term will be used in the treatment-emergent computation. A TEAE, defined as an event that first occurred or worsened in severity after baseline, will be summarized by SOC and by decreasing frequency of preferred term within SOC.

Laboratory and nonlaboratory CTCAEs will be summarized by CTCAE term and maximum CTCAE grade, including the total for maximum Grades 3 and 4. These summaries will be provided for events regardless of study drug causality and will be repeated for events deemed by the investigator to be possibly related to study medication.

Reasons for death will be summarized separately for on-therapy and within 30 days of last dose of study drug. SAEs will be summarized by preferred term.

Hospitalizations and transfusions during the study treatment period or during the 30-day safety follow-up period will be summarized by treatment group.

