Relative Day Within a Cycle	≤28	≤14	≤7	1 c,d	8 c	14 c	15	22	1 c	14 c,e	22	1 c			14 c,e
Fibrotest		X				X				X			X		
aPTT/PT/INR		X		X					X			X			
Patient-reported outcomes															
EORTC QLQ-30		X							X			X		X	
EORTC QLQ-HCC 18		X							X			X		X	
Resource utilization									X			X		X	Document BSC measures, concomitant medications, transfusions, and treatment-related hospitalization days
Translational research															
Whole blood for PGx				X											

Cycle (Visit)	Baseline (Visit 0)			Patient on Study Treatment									Post Discontinuation Followup Periods		Comments	
				Cycle 1 (Visit 1)			Cycle 2 (Visit 2)			Cycle 3, n a (Visit 3, etc)			30-Day Safety Follow-Up (v801)	Long Term Follow-Up b (v802, v803, etc)		
Relative Day Within a Cycle	≤28	≤14	≤7	1 c,d	8 c	14 c	15	22	1 c	14 c,e	22	1 c			14 c,e	
Optional tumor biopsy	X									X				X n		± 3 days Optional tumor biopsy to be obtained at baseline, cycle 2 and after end of treatment with LY2157299
Obtain diagnostic tumor tissue	X															Mandatory for study entry. Tumor tissue (tumor blocks or slides) must be located prior to randomization and sent to central laboratory after randomization

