6.12.5. Hospitalizations and Blood Transfusions

Hospitalizations and blood transfusions will be collected during the study treatment period and during the 30-day post discontinuation follow-up period (Visit 801).

The number of subjects requiring hospitalization, the number of hospitalizations per subject, and duration of hospital stay for each event and for each subject will be summarized by treatment group using descriptive statistics. Any patients with a hospitalization admission and discharge date on the same day are counted as a half-day in the duration of hospitalization. End dates will be imputed as the data cutoff date for patients with hospitalization ongoing at the time of analysis.

A listing of all patients who were hospitalized will be provided. The listing will include the reason for hospitalization (that is, AE, protocol test, or other), MedDRA PT, start and end dates, and duration of hospitalization.

The number of prior, concomitant, and post-discontinuation blood transfusions and transfused units per subject will be summarized by the type of blood product transfused (that is, packed red blood cells, whole blood, platelets, fresh frozen plasma, or other).

Additionally, patients that received prior, concomitant, and post-discontinuation transfusions will be listed. The listing will include the date of transfusion, type of blood products received, number of units transfused, and MedDRA PT for each patient.

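### Protocol 10.2.2 and the Study Schedule limit recorded hospitalization days to treatment-related ones, while the objective and SAP 6.12.5 cover hospitalizations without that limit; stays due to progression may be missed

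*Protocol*

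**What the plan says.** Two places in the protocol tell sites what to enter for resource utilization, and both carry a limiter.

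- Section 10.2.2: "Investigators will be asked to document the use of best supportive care measures, concomitant medications, transfusions, and treatment-related hospitalization days".
- Attachment 1, comment on the resource-utilization row: "Document BSC measures, concomitant medications, transfusions, and treatment-related hospitalization days".

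Four places describe what is to be assessed, collected or analysed, and none carries it.

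- Protocol 6.3, exploratory objective: "to assess healthcare resource utilization including transfusions and hospitalizations".
- Protocol 10.3.2.1: "Other safety measures include assessments of physical examinations, preexisting conditions, transfusions and hospitalizations, and AEs".
- Protocol 12.2.11: "Hospitalizations and transfusions during the study treatment period or during the 30-day safety follow-up period will be summarized by treatment group".
- SAP 6.12.5 says that hospitalizations are collected on treatment and through Visit 801. It then summarises by treatment group "The number of subjects requiring hospitalization, the number of hospitalizations per subject, and duration of hospital stay for each event" and for each subject. Its listing gives the reason for each stay in three categories: adverse event, protocol test, or other.

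**The concern.** The instruction to sites is narrower than the quantity the SAP says it will tabulate. A coordinator working from 10.2.2 or the schedule would leave out a stay that the investigator did not attribute to treatment. The by-arm table would still be headed as hospitalizations.

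Two consequences follow if that happens. First, admissions driven by the cancer itself, which an effective treatment might reduce, are the ones most exposed to omission. Second, whether a stay is counted depends on an attribution. Protocol 9.5 makes Arm 1 open label, so there the attribution is made with full knowledge of treatment. Protocol 8.2 gives safety comparison with sorafenib as the purpose of the monotherapy arm, and 12.2.11 puts the hospitalization summary among the safety analyses, so contrasts with Arm 1 are where this would matter.

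**Working it through.** No sample size, power or event figure is involved, so the check is a comparison of texts followed by a trace of each type of stay.

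**1. Is the difference one of scope or of time window?** Protocol 10.2.2 collects through the 30-day safety follow-up visit. Protocol 12.2.11 and SAP 6.12.5 use the treatment period plus the same 30 days. The windows agree; only the scope differs.

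**2. Could the limiter be a slip?** It stands in both places that define the resource-utilization record. Within 10.2.2 it qualifies hospitalization days but not transfusions or concomitant medications. Read plainly, it is an instruction.

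**3. Could a record limited in this way fill the SAP outputs?** Not fully. A protocol-test admission is not treatment-related in any ordinary sense, yet the SAP has a category for it. The SAP also needs the number of stays per subject, stay durations, and a half-day rule for same-day discharge. These need admission and discharge dates, not a count of days.

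**4. Which stays have another route into the database?** Inpatient hospitalization is a seriousness criterion (Protocol 10.3.1.1), and Table JBAS.10.2 asks for all serious events on treatment and in the 30-day follow-up. The same section exempts serious events due to disease progression unless the investigator considers them possibly drug-related. It also excludes planned admissions for pre-existing conditions and admissions with no precipitating clinical event.

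| Type of stay | Record under 10.2.2 as written | Serious adverse event report |
|---|---|---|
| Judged treatment-related | Yes | Yes |
| Adverse event, judged unrelated, not due to progression | No | Yes |
| Due to progression, not thought possibly drug-related | No | No |
| Protocol procedure or planned, no precipitating event | No | No |

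The third row is the substantive gap: such stays are outside both routes. The second row is lost from the resource-utilization record but not from the trial data.

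**5. What decides the row?** The investigator's judgement of relatedness, at both routes for a progression-related stay. Protocol 10.3.1 defines relatedness for adverse events and counts an unknown relationship as related. Nothing says whether that rule applies to hospitalization days.

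**6. Can the loss be sized?** No. The documents give no hospitalization rate and no split of stays by cause. The loss could be nil, if the form and its instructions were broader than 10.2.2. At the other extreme it could be every progression stay not thought possibly drug-related.

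**The case against.** The strongest reply is that a reader might infer that the trial collects only treatment-related stays, and the documents do not show this. Protocol 10.3.2.1 lists hospitalizations as a safety measure without a limiter. SAP 6.12.5 is a statement about collection as well as analysis, and its reason categories suggest a form that was not restricted. The hospitalization form is not among the documents, so actual loss of data is an inference. This stands: what is established is an instruction that conflicts with other parts of the plan, not a proven gap in the data.

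It is also fair to say that the serious adverse event route does a good deal. Bleeding or liver decompensation judged unrelated to drug, and not due to progression, is reportable whatever the attribution. That narrows the exposed group to progression stays, plus the planned and procedural admissions that matter less here.

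Finally, the measure is exploratory, no hypothesis is tested on it, and the comparison of Arm 2 with Arm 3 is blinded to LY2157299 or placebo with sorafenib in both arms. That is correct, and it limits the open-label concern to contrasts with Arm 1.

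None of this removes the contradiction. If the form is broader than 10.2.2, sites still hold two instructions telling them to record less. Completeness could then vary between sites, and the table would mix two definitions.

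**Conclusion.** The point holds as an inconsistency between what sites are told to record and what the objective, Protocol 12.2.11 and SAP 6.12.5 treat as the measure. Any loss depends on two conditions that the documents leave open: that sites follow 10.2.2 and the schedule literally, and that the case report form does not ask for more. Under those conditions, progression stays not thought possibly drug-related are missing, and inclusion turns on a judgement that is unblinded in Arm 1.

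Two stronger readings are not supported.

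- A reader might infer that most disease-related stays are missing, taking as a proxy the 45 of 155 serious events considered related to LY2157299 in the protocol's summary of clinical experience (45/155 = 29%, leaving 71%). Those are serious events across the program, not hospitalizations in this trial, and they do not measure attribution to sorafenib. The other 110 (155 − 45) were reported, so they are not evidence of unreported stays.
- A reader might infer a bias in a known direction: sorafenib's listed reactions in Attachment 18 include gastrointestinal hemorrhage and raised bilirubin, which can resemble complications of the disease, so stays in Arms 2 and 3 might more readily be called treatment-related. That is plausible but not demonstrated.

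The effect is confined to an exploratory objective and a descriptive by-arm safety summary. The overall survival analysis is untouched. The change is still worth making because it is cheap and alters what is counted.

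**What to change.** - In Protocol 10.2.2 and the Attachment 1 comment, drop the treatment-related qualifier. Ask for all hospitalizations, with admission date, discharge date and a reason. This matches SAP 6.12.5.
- Add disease progression to the reason categories in the form and in the SAP 6.12.5 listing, so that these stays are not hidden under other.
- If treatment-related stays are of interest, show them as a subset and state which relatedness rule applies.
- If the narrow scope was intended, the alternative is to restrict the objective, Protocol 12.2.11 and SAP 6.12.5 to treatment-related stays and define the term.
- For data already collected, first check the case report form and its completion instructions. Relabel or footnote the SAP table only if collection was in fact restricted; relabelling without that check could misdescribe a complete record.

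The cost is a wording change in two protocol places, one added reason category and a few more form entries per admission. If no further data can be added, it is the form check and possibly a footnote.

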### 10.3. Safety Evaluations

Investigators will be responsible for monitoring the safety of patients who have entered this study and for alerting Lilly or its designee to any event that seems unusual, even if this event may be considered an unanticipated benefit to the patient.

The investigator will be responsible for the appropriate medical care of patients during the study.

The investigator will remain responsible for following, through an appropriate healthcare option, AEs that are serious, that are considered related to the study, or that caused the patient to discontinue before completing the study. The patient should be followed until the event is resolved or explained. Frequency of follow-up evaluation is left to the discretion of the investigator.

The timing of all safety evaluations is shown in the Study Schedule ([Attachment 1](#)).

[Table JBAS.10.2](#) describes AE and SAE collection with regard to the type of events to be reported during each period of the study.

**Table JBAS.10.2. Adverse Event and Serious Adverse Event Reporting Guidelines**

Period	Types of AEs/SAEs to be Reported
Baseline (pretreatment)	Preexisting conditions All AEs SAEs related to protocol procedures
Study treatment period	All AEs and SAEs
30-day safety follow-up	All AEs and SAEs
Long-term follow-up	All SAEs related to protocol procedures or study drugs
Extension period	All AEs and SAEs
Extension period follow-up	All AEs and SAEs
After the patient is no longer participating in the study (that is, no longer receiving study therapy and no longer in follow-up)	All SAEs related to protocol procedures or study drugs that the investigator becomes aware of

Abbreviations: AE = adverse event; SAE = serious adverse event.

### 10.3.1. Adverse Events

Lilly has standards for reporting AEs that are to be followed regardless of applicable regulatory requirements that may be less stringent. A clinical study AE is any untoward medical event associated with the use of a drug in humans, whether or not it is considered related to that drug.

Lack of drug effect is not an AE in clinical trials, because the purpose of the clinical trial is to establish drug effect.

Any clinically significant findings from ECGs, laboratory values, vital sign measurements, or other procedures that result in a diagnosis should be reported to Lilly or its designee.

Cases of pregnancy that occur during maternal or paternal exposures to study drug should be reported. Data on fetal outcome and breast-feeding are collected for regulatory reporting and drug safety evaluation.

Study site personnel will record the occurrence and nature of each patient's preexisting conditions, including clinically significant signs and symptoms of the disease under treatment in the study.

After the ICF is signed, site personnel will record in the electronic CRF (eCRF) any change in the condition(s) and the occurrence and nature of any AEs. All AEs related to protocol procedures are reported to Lilly or its designee via eCRF.

In addition, all AEs occurring after the patient receives the first dose of study drug must be reported to Lilly or its designee via eCRF.

Any clinically significant findings from ECGs, laboratory tests, vital-sign measurements, other procedures, and so on that result in a diagnosis should be reported to Lilly or its designee via eCRF.

Investigators will be instructed to report to Lilly or its designee their assessment of the potential relatedness of each AE to protocol procedure, studied disease state, and/or study drug via eCRF.

If a patient's dosage is reduced or treatment is discontinued as a result of an AE, study-site personnel must clearly report to Lilly or its designee via eCRF the circumstances and data leading to any such dosage reduction or discontinuation of treatment.

The investigator will interpret the observed AEs as related to disease, to the study medication, study procedure, or other concomitant treatment or pathologies. To assess the relationship of the AE to the study drug or procedure, the following terminologies are defined:

- **Probably related:** a direct cause-and-effect relationship between the study treatment and the AE is likely
- **Possibly related:** a cause-and-effect relationship between the study treatment and the AE has not been demonstrated at this time and is not probable but is also not impossible
- **Does not know:** the investigator cannot determine
- **Not related:** without question, the AE is definitely not associated with the study treatment

The investigator should classify all “probably related,” “possibly related,” or “does not know” AEs and SAEs as related to study drug/study procedure.

Patients will be evaluated for AEs at each visit and will be instructed to call their physician to report any AEs between visits.

The National Cancer Institute (NCI)-CTCAE version 4.0 will serve as the reference document for choosing appropriate terminology for, and grading the severity of, all AEs and other symptoms. For AEs without matching terminology within the NCI-CTCAE version 4.0 criteria, the investigator will be responsible for selecting the appropriate system organ class (SOC) and assessing severity grade based on the intensity of the event.

In addition to collecting the AE verbatim and the CTCAE severity grade, AE verbatim text will also be mapped by Lilly or its designee to corresponding terminology within the *Medical Dictionary for Regulatory Activities* (MedDRA) dictionary.

